3.2 DISCUSSION OF TRIAL DESIGN, INCLUDING THE CHOICE OF CONTROL GROUP

This is a standard design of a (C-14) human mass balance trial to determine absorption, metabolism, and excretion of BI 1265162.

The inclusion of a control group is not required for such an investigation.

The elimination of BI 1265162 is multi-exponential. The terminal mean half-life with 15.5h seems to be moderate. If drug can be absorbed all through the gastro-intestinal tract, this may result in low systemic concentrations for a longer period of time. Therefore, it cannot be excluded that prolonged sampling is necessary in humans. Hence, after 8 in-house days after dosing during which excreta will be collection, subjects will return for in-house 24-h collection intervals on a weekly basis for up to 4 weeks after dosing as long as release criteria are not met (see also [Section 3.1](#)).

The open-label treatment is not expected to bias results because all subjects receive the same treatment within each trial part and the main trial endpoints are derived from measurements of plasma, urine and faeces concentrations of analytes which are provided by a bioanalytical laboratory.

3.3 SELECTION OF TRIAL POPULATION

It is planned that 7 healthy male subjects will enter each trial part, i.e. in total 14 subjects. They will be recruited from the subject-pool of the trial site.

Only male subjects will be included in the trial to reduce variability of results.

The current trial is designed to investigate the basic pharmacokinetics of BI 1265162 including absorption, metabolism, and elimination and quantitative determination of excretion by mass balance. Samples will be generated for additional metabolic profiling and structural identification. Healthy male subjects are an ideal population for the objectives of this trial, since they provide relatively stable physiological, biochemical and hormonal conditions, i.e. the absence of disease-related variations and relevant concomitant medications.

A log of all subjects enrolled into the trial (i.e. who have signed informed consent) will be maintained in the ISF irrespective of whether they have been treated with investigational drug or not.

3.3.1 Main diagnosis for trial entry

The trial will be performed in healthy male subjects.

3.3.2 Inclusion criteria

Subjects will only be included in the trial if they meet the following criteria:

1. Healthy male subjects according to the assessment of the investigator, as based on a complete medical history including a physical examination, vital signs (BP, PR), 12-lead ECG, and clinical laboratory tests
2. Age of 18 to 65 years (inclusive)
3. BMI of 18.5 to 29.9 kg/m² (inclusive)
4. Signed and dated written informed consent prior to admission to the trial, in accordance with GCP and local legislation
5. Subjects who are sexually active must use, with their partner, highly effective contraception from the time of administration of trial medication until 3 months after administration of trial medication. Adequate methods are:
 - Condoms plus use of hormonal contraception by the female partner that started at least 2 months prior to administration of trial medication (e.g., implants, injectables, combined oral or vaginal contraceptives, intrauterine device), or
 - Condoms plus surgical sterilization (vasectomy at least 1 year prior to enrolment), or

Proprietary confidential information © 2020 Boehringer Ingelheim International GmbH or one or more of its affiliated companies

- Condoms plus surgically sterilised partner (including hysterectomy), or
- Condoms plus intrauterine device, or
- Condoms plus partner of non-child bearing potential (including homosexual men)

Subjects are required to use condoms to prevent unintended exposure of the partner to the trial drug via seminal fluid.

Alternatively, true abstinence is acceptable when it is in line with the subject's preferred and usual lifestyle. If a subject is usually not sexually active but becomes active, with their partner, they must comply with the contraceptive requirements detailed above.

3.3.3 Exclusion criteria

Subjects will not be allowed to participate, if any of the following general criteria apply:

1. Any finding in the medical examination (including BP, PR or ECG) deviating from normal and assessed as clinically relevant by the investigator
2. Repeated measurement of systolic blood pressure outside the range of 90 to 139 mmHg, diastolic blood pressure outside the range of 45 to 89 mmHg, or pulse rate outside the range of 40 to 100 bpm
3. Any laboratory value outside the reference range that the investigator considers to be of clinical relevance
4. Any evidence of a concomitant disease assessed as clinically relevant by the investigator
5. Clinically significant gastrointestinal, hepatic, renal, respiratory, cardiovascular, metabolic, immunological or hormonal disorders
6. Cholecystectomy or other surgery of the gastrointestinal tract that could interfere with the pharmacokinetics of the trial medication (except appendectomy or simple hernia repair)
7. Diseases of the central nervous system (including but not limited to any kind of seizures or stroke), and other relevant neurological or psychiatric disorders
8. History of relevant orthostatic hypotension, fainting spells, or blackouts
9. Chronic or relevant acute infections
10. History of relevant allergy or hypersensitivity (including allergy to the trial medication or its excipients)
11. Use of drugs within 30 days of planned administration of trial medication that might reasonably influence the results of the trial (including drugs that cause QT/ QTc interval prolongation)
12. Intake of an investigational drug in another clinical trial within 60 days of planned administration of investigational drug in the current trial, or concurrent participation in another clinical trial in which investigational drug is administered
13. Smoking habit other than incidental. Incidental smoker is defined as a person who will not smoke more than 5 cigarettes per week
14. Inability to refrain from smoking in the clinical research unit

Proprietary confidential information © 2020 Boehringer Ingelheim International GmbH or one or more of its affiliated companies

15. Alcohol abuse (average intake of more than 24 units of alcohol per week (1 unit of alcohol equals approximately 250 mL of beer, 100 mL of wine or 35 mL of spirits))
16. Drug abuse or positive drug screening
17. Blood donation of more than 100 mL within 30 days of planned administration of trial medication or intended blood donation during the trial
18. Intention to perform excessive physical activities within 96 hours prior to the administration of trial medication and during the trial until the discharge at Day 9
19. Inability to comply with the dietary regimen of the trial site
20. A marked baseline prolongation of QT/QTc interval (such as QTc intervals that are repeatedly greater than 450 ms) or any other relevant ECG finding at screening
21. A history of additional risk factors for *Torsade de Pointes* (such as heart failure, hypokalaemia, or family history of Long QT Syndrome)
22. Subject is assessed as unsuitable for inclusion by the investigator, for instance, because the subject is not considered able to understand and comply with trial requirements, or has a condition that would not allow safe participation in the trial

In addition, the following trial-specific exclusion criteria apply:

23. A history of chronic kidney disease
24. Participation in another ADME study with a radiation burden of 0.1-1.0 mSv in the period of 1 year prior to screening or 1.1-2.0 mSv in the past 2 years or 2.1-3.0 mSv in the past 3 years etc.
25. Exposure to radiation for diagnostic reasons (except dental X-rays and plain X-rays of thorax and bony skeleton (excluding spinal column) in the period of 1 year prior to screening)
26. Irregular defecation pattern (less than a mean of one bowel movement every other day)

For trial restrictions, see [Section 4.2.2](#).

3.3.4 Withdrawal of subjects from treatment or assessments

Subjects may discontinue trial treatment or withdraw consent to trial participation as a whole ('withdrawal of consent') with very different implications; see [Sections 3.3.4.1](#) and [3.3.4.2](#) below.

If a subject is removed from or withdraws from the trial prior to the first administration of trial medication, the data of this subject will not be entered in the case report form (CRF) and will not be reported in the clinical trial report (CTR). If a subject is removed from or withdraws from the trial after the first administration of trial medication, this will be documented and the reason for discontinuation must be recorded in the CRF; in addition, the data will be included in the CRF and will be reported in the CTR. At the time of discontinuation, a complete end of trial examination will be performed, if possible, and the information will be recorded in the CRF. If the discontinuation occurs before the end of the REP (see [Section 1.2.6](#)), the discontinued subject should, if possible, be questioned for AEs and concomitant therapies at or after the end of the REP in order to ensure collection of AEs

Proprietary confidential information © 2020 Boehringer Ingelheim International GmbH or one or more of its affiliated companies

and concomitant therapies throughout the REP, if not contrary to any consent withdrawal of the subject.

3.3.4.1 Removal of individual subjects

An individual subject will be removed from the trial if:

1. The subject wants to discontinue trial treatment, without the need to justify the decision
2. The subject has repeatedly shown to be non-compliant with important trial procedures and, in the opinion of both, the investigator and sponsor representative, is not willing or able to adhere to the trial requirements in the future.
3. The subject needs to take concomitant medication that interferes with the investigational medicinal product or other trial treatment
4. The subject can no longer receive trial treatment for medical reasons (such as surgery, adverse events [AEs], or diseases)
5. The subject has an elevation of AST and/ or ALT \geq 3-fold ULN and an elevation of total bilirubin \geq 2-fold ULN (measured in the same blood sample) and/ or needs to be followed up according to the DILI checklist provided in the ISF

In addition to these criteria, the investigator may discontinue subjects at any time based on his or her clinical judgment.

Even if the trial treatment is discontinued, the subject remains in the trial and, given his agreement, will undergo the procedures for early treatment discontinuation and follow up as outlined in the [Flow Chart](#) and [Section 6.2.3](#).

3.3.4.2 Withdrawal of consent to trial participation

Subjects may withdraw their consent to trial participation at any time without the need to justify the decision. If a subject wants to withdraw consent, the investigator should be involved in the discussion with the subject and explain the difference between trial treatment discontinuation and withdrawal of consent to trial participation, as well as explain the options for continued follow up after trial treatment discontinuation. For details, see [Section 3.3.4.1](#).

3.3.4.3 Discontinuation of the trial by the sponsor

Boehringer Ingelheim reserves the right to discontinue the trial at any time for any of the following reasons:

1. Failure to meet expected enrolment goals overall or at a particular trial site
2. New toxicological findings, serious adverse events, or any safety information invalidating the earlier positive benefit-risk-assessment. More specifically, the trial will be put on hold, and only proceed after mutual consultation between the Sponsor and the Principal Investigator, if more than 50% of the subjects have drug-related and clinically relevant adverse events of moderate or severe intensity, or if 1 or more drug-related serious adverse event is reported.
3. Violation of GCP, or the CTP, or the contract with BI impairing the appropriate conduct of the trial

Proprietary confidential information © 2020 Boehringer Ingelheim International GmbH or one or more of its affiliated companies

4. The sponsor decides to discontinue the further development of the investigational product.

The investigator/ trial site will be reimbursed for reasonable expenses incurred in case of trial termination (except, if item 3 applies).

3.3.5 Replacement of subjects

In case subjects in either trial part do not complete the trial, the Trial Clinical Leader together with the Trial Pharmacokineticist and the Trial Statistician are to decide, if and how many subjects will be replaced. A replacement subject will be assigned a unique trial subject number, and will be assigned to the same treatment as the subject he replaces.

4. TREATMENTS

4.1 INVESTIGATIONAL TREATMENTS

Radiolabelled BI 1265162 is administered as a solution of BI 1265162 (C-14). The oral and intravenous solution contains (C-14) BI 1265162 and unlabelled BI 1265162 which is manufactured by BI Pharma GmbH & Co. KG. The final drug product oral solution and intravenous solution is made by [REDACTED].

4.1.1 Identity of the Investigational Medicinal Products

The characteristics of the test product are given below:

(Part 1) Intravenous BI 1265162 (C-14)

Name: BI 1265162 (C-14) intravenous solution 5 µg/mL (10 mL; 0.018 MBq)
Substance: BI 1265162 and (C-14) BI 1265162
Pharmaceutical formulation: Intravenous solution
Source: [REDACTED]
Unit strength: 50 µg
Posology: 1-0-0
Route of administration: Intravenous
Duration of use: Single dose

(Part 2) Oral BI 1265162 (C-14)

Name: BI 1265162 (C-14) oral solution 0.25 mg/mL (20 mL; 0.306 MBq)
Substance: BI 1265162 mixed with (C-14) BI 1265162
Pharmaceutical formulation: Oral solution
Source: [REDACTED]
Unit strength: 5 mg
Posology: 1-0-0
Route of administration: Oral
Duration of use: Single dose

The characteristics of the reference product are given below:

Not applicable.

4.1.2 Selection of doses in the trial

(Part 1) Intravenous BI 1265162 (C-14)

The intravenous dose of 50 µg BI 1265162 (C-14) is expected to yield exposures that will be similar to the systemic exposure which is achieved with a dose of 200 µg administered by inhalation, the highest dose being tested in phase II trials (1399-0003). This dose is below the already tested highest doses (single doses up to 1200 µg, multiple doses up to 75 µg BID (150 µg/d)) of BI 1265162 in healthy subjects. In healthy subjects, a single dose of 1200 µg was safe and well-tolerated ([Section 1.3](#)).

This dose, administered as intravenous solution, will include 0.018 MBq of BI 1265162 (C-14). The radiolabelled dose of 0.018 MBq is required for the objectives of the trial, i.e. to provide good detection limits for measurement of radioactivity in urine, faeces and plasma. The total effective dose (radiation burden) amounts to 0.001 mSv. This is below the limit of ICRP Category 1 and considered acceptable [[R15-3219](#)].

Radiation burden calculations are presented in [Appendix 10.1](#). For risk-benefit assessment, see [Section 1.4](#).

(Part 2) Oral BI 1265162 (C-14)

The oral dose of 5 mg BI 1265162 (C-14) was chosen on the ground of preliminary results from the ongoing absolute bioavailability trial 1399-0014 (refer to [Section 1.4](#)). Since developed for inhalative administration, BI 1265162 has not been applied in an oral fashion. An oral dose of 5 mg is considered to be adequate for the objectives of the current trial.

This dose, administered as oral solution, will include 0.306 MBq of BI 1265162 (C-14). The radiolabelled dose of 0.306 MBq is required for the objectives of the trial providing good detection limits for measurement of radioactivity in urine, faeces and plasma. The total effective dose (radiation burden) amounts to 0.0014 mSv. This is below the limit of ICRP Category 1 and considered acceptable.

Radiation burden calculations are presented in [Appendix 10.1](#). For risk-benefit assessment, see [Section 1.4](#).

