1.3 RATIONALE FOR PERFORMING THE TRIAL

Rationale for trial

The development of BI 1265162 was optimized for inhalation. However, as the application of inhaled radio-labelled substance is technically challenging, the intravenous application of BI 1265162 (C-14) will mimic the systemic exposure as if the compound was inhaled. The oral dose investigates the absorption and metabolism of the swallowed portion of the inhaled dose.

Therefore, this trial will be performed in 2 parts to characterize by means of mass balance

- (Part 1) basic pharmacokinetics, metabolism (metabolic profile) and routes of elimination of BI 1265162 (C-14) after intravenous administration, and
- (Part 2) the extent of gastrointestinal absorption, metabolism (metabolic profile), and routes of elimination of BI 1265162 (C-14) after oral administration.

The oral application of BI 1265162 (C-14) is intended to determine the extent of absorption of BI 1265162 and/ or its metabolites from the gastrointestinal tract. Due to the optimization of BI 1265162 for inhalation, this oral fraction is small (see also [Table 1.3: 1](#)). If metabolites will be formed in the gastro-intestinal tract and absorbed into the systemic circulation, their presence will be detected.

The data are required for future regulatory interactions, to further understand the pharmacokinetics of BI 1265162, including the quantitative determination of elimination pathways and drug metabolites.

Rationale for dose selection

The dose selection is based on previous experience with orally, inhaled and intravenously applied BI 265162 in healthy male subjects.

(i) Rationale for the intravenous dose

According to preliminary results of study 1399-0014, the single intravenous dose of 50 µg of BI 1265162 was well tolerated and safe. Comparing systemic exposures after the inhaled (trial 1399-0001, [Table 1.2.4: 1](#)) and intravenous (1399-0014, [Table 1.2.4: 2](#)) application of BI 1265162, mean C_{max} and AUC values after the intravenous application of 50 µg should correspond to those after the inhalation of 300 µg to 600 µg, and 600µg to 1200 µg, respectively. All doses were well tolerated and safe. The infusion time of 1 hour was chosen to limit the peak exposure and to better mimic the exposure after inhalation.

(ii) *Rationale for the oral dose*

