According to preliminary results of study 1399-0014, the single oral dose of 1.25 mg of BI 1265162 seemed to be well tolerated and safe. The SAE was not assessed to be related to the oral application of BI 265162. Since the systemic exposure was lower than expected, the application of a 5 mg dose of BI 1265162 was chosen to achieve a meaningful systemic exposure in this study. For the pharmacokinetic rationale, see below.

However, an oral BI 1265162 dose of 5 mg has not been applied in humans before. A de-novo estimation of a safe starting dose was performed by applying the relevant algorisms of the FDA guidance ‘Estimating the Maximum Safe Starting Dose in Initial Clinical Trials for Therapeutics in Adult Healthy Volunteers’ [R06-1037] and the ICH guideline M3(R2) on ‘Non-clinical Safety Studies for the Conduct of Human Clinical Trials and Marketing Authorisation for Pharmaceuticals’ [R15-0594]. The results are displayed in [Table 1.3: 1](#) along with the relevant pharmacokinetics obtained from human studies.

Table 1.3: 1 Estimation of safe starting doses based on toxicological results in rats and dogs exposed to BI 1265162

	Human	Dog	Rat
FDA Approach			
NOAEL [mg/kg]		10	100
NOEL[mg/kg]		3	
Conversion Factor		1.8	6.2
HED for 60 kg Human (NOAEL) [mg]		333	967
HED for 60 kg Human (NOEL) [mg]		99.6	
Safety Factor of 10 on HED (NOAEL) [mg]		33.3	96.7
Safety Factor of 10 on HED (NOEL) [mg]		9.96	
ICH M3(R2) Approach			
HED for 60 kg Human (NOAEL) [mg]		333	967
C_{max} at NOAEL [pmol/L] at Day 1		M: 927,000; F: 458,000	
AUC at NOAEL [pmol·h/L] at Day 1		M: 2,620,000; F: 1,300,000	
HED for 60 kg Human (NOEL)		99.6 mg	
C_{max} at NOEL [pmol/L] at Day 1		M: 228,000; F: 234,000	
AUC at NOEL [pmol·h/L] at Day 1		M: 655,000; F: 544,000	
Safety Factor of 50 on C_{max} (NOEL) [pmol/L]		M: 4,560; F: 4,680	
Safety Factor of 50 on AUC (NOEL) [pmol·h/L]		M: 13,100; F: 10,800	
Human pharmacokinetic parameters (gMean (gCV) after single doses of BI 1265162			
1399-0001			
C_{max} after 1200 µg inhaled [pmol/L]		6500 (73.1)	
AUC after 1200 µg inhaled [pmol·h/L]		3920 (76.4)	
1399-0014 (ongoing)*			
1.25 mg PO (N=4)			
C_{max} [pmol/L]		57.7 (69.0)	
$AUC_{0-\infty}$ [pmol·h/L]		316 (83.5)	
50 µg IV (N=4)			
C_{max} [pmol/L]		1880 (8.79)	
$AUC_{0-\infty}$ [pmol·h/L]		2200 (12.2)	
Absolute bioavailability[%]		0.6	

* Preliminary, not validated data; subject to change!

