4. CHANGES IN THE PLANNED ANALYSIS OF THE STUDY

Recruitment stopped after Part 1 due to COVID-19 pandemic. Before the planned re-start of recruitment into Part 2, the study was prematurely stopped as Boehringer Ingelheim decided not to further develop the compound BI 1265162.

Consequently, only a subset of the analyses planned in the CTP will be performed, and only data from Part 1 (intravenous administration of the compound) will be analysed. For all study endpoints, listings will be provided. Tables will be provided for disposition, demography and adverse events (including one of the secondary endpoints) as well as for mass balance and PK endpoints (including the primary and all further secondary endpoints). For variables regarding medical history, concomitant medication and non-drug procedures, exposition, protocol deviations, laboratory data, vital signs and local tolerability, only listings will be provided and no descriptive analysis will be carried out.

In CTP section 7.3 the following was defined: *Important protocol deviation (iPD) categories will be specified in the Integrated Quality and Risk Management Plan, iPDs will be identified no later than in the Report Planning Meeting, and the iPD categories will be updated as needed.*

Due to SOP changes, the iPD categories are no longer available in the IQRM plan but included in an iPD specification file (3). The iPD categories originally defined in IQRM plan were transferred to the iPD specification file. Minor changes regarding the iPD categories were performed only.

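### Do the two different inhaled equivalents given for the 50 µg intravenous dose call for a change to the plan?

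*Protocol*

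**What the plan says.** Section 1.3 of the protocol (rationale for the intravenous dose) compares trial 1399-0014 (intravenous) with trial 1399-0001 (inhaled). It concludes that mean Cmax and AUC after 50 µg intravenously "should correspond to those after the inhalation of 300" to 600 µg for Cmax, and of 600 to 1200 µg for AUC. It adds that the single intravenous dose of 50 µg "of BI 1265162 was well tolerated and safe" in 1399-0014, on preliminary results.

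Section 4.1.2 says the same intravenous dose should give exposure "similar to the systemic exposure which is achieved with a dose of 200" µg by inhalation, and calls that inhaled dose "the highest dose being tested in phase II trials". It does not separate Cmax from AUC. It continues: "This dose is below the already tested highest doses (single doses up to 1200" µg, and "multiple doses up to 75" µg twice daily).

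Table 1.3: 1 gives geometric means for both routes. Its footnote marks the 1399-0014 figures as "Preliminary, not validated data; subject to change".

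Section 4 of the SAP states that "only data from Part 1 (intravenous administration of the compound) will be analysed".

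**The concern.** Two sections that justify the same dose give incompatible inhaled equivalents, and 200 µg falls below the lower bound of both Section 1.3 ranges. The intravenous route was chosen to stand in for systemic exposure after inhalation, so the inhaled match is part of the reason for Part 1, and Part 1 is the only part that will be reported. On Section 4.1.2, a reader would take Part 1 exposure to match the highest phase II dose. On Section 1.3, the reader would take it to be above that dose. If a planned comparison, an exposure limit or a tolerability argument rested on the 200 µg figure, the slip would matter.

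**Working it through.** **Inputs** (Table 1.3: 1, geometric mean with gCV %)

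| | Cmax, pmol/L | AUC, pmol·h/L |
|---|---|---|
| 50 µg intravenous (N=4, preliminary; AUC to infinity) | 1880 (8.79) | 2200 (12.2) |
| 1200 µg inhaled (AUC type not stated in the table) | 6500 (73.1) | 3920 (76.4) |

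**1. The two statements side by side.** Section 1.3 range divided by 200 µg:
- Cmax: 300/200 = 1.5 and 600/200 = 3.
- AUC: 600/200 = 3 and 1200/200 = 6.

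The conflict needs no model.

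**2. Can the table reproduce either statement?** Assume inhaled exposure is proportional to dose. The public text does not state this.
- Section 1.3, Cmax: 300–600 µg scales to 6500 × 300/1200 = 1625 and 6500 × 600/1200 = 3250, which contains 1880.
- Section 1.3, AUC: 600–1200 µg scales to 3920 × 600/1200 = 1960 and 3920, which contains 2200.
- Section 4.1.2: 200 µg scales to 6500/6 = 1083 and 3920/6 = 653. The intravenous means are 1880/1083 = 1.74 and 2200/653 = 3.37 times these.
- Equivalent inhaled dose: 1200 × 1880/6500 = 347 µg (Cmax); 1200 × 2200/3920 = 673 µg (AUC).

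So Section 1.3 is reproduced and Section 4.1.2 is not.

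**3. How far this depends on proportionality.** Let exposure vary as dose to the power b. The equivalent dose is 1200 × (IV mean / inhaled mean)^(1/b).

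| b | Cmax, µg | AUC, µg |
|---|---|---|
| 0.7 | 204 | 526 |
| 0.8 | 255 | 583 |
| 0.9 | 302 | 632 |
| 1.0 | 347 | 673 |
| 1.3 | 462 | 770 |

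For 200 µg to match, b must be ln(6500/1880)/ln 6 = 0.69 on Cmax and ln(3920/2200)/ln 6 = 0.32 on AUC. No single b gives 200 µg on both. At b = 0.8 or below, the Section 1.3 ranges are not reproduced either.

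**4. A more generous reading of 200 µg.** If it meant 200 µg twice daily, the scaled 24-hour AUC would be 2 × 653 = 1307, and 2200/1307 = 1.7. The gap narrows but remains.

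**5. Does the comparison with 1200 µg inhaled survive?** It uses observed means and needs no scaling: 1880/6500 = 0.29 and 2200/3920 = 0.56. Both are below 1, whichever equivalent is used.

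**6. What depends on the equivalence?**
- Primary endpoints (protocol Section 2.1.2): radioactivity recovered as a percentage of the dose given. No inhaled reference enters.
- Secondary endpoints (Section 2.1.3): AUC and Cmax as measured, and the percentage of subjects with drug-related adverse events. No inhaled reference enters.
- Analysis sets (Section 7.3; SAP Section 6.3): none is defined by exposure relative to inhalation.
- SAP Sections 7, 7.4 and 7.5: descriptive statistics, with no comparison against inhaled data in the visible text.
- Sample size (Section 7.7): no power calculation.

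**The case for a change.** The strongest case for acting is that both statements are current protocol text, both are legible, and the correction would cost only a sentence. Someone drawing the trial report from Section 4.1.2 could describe Part 1 as matching the highest phase II exposure, which the protocol's own table does not support under proportionality. On AUC, 200 µg would need a slope of about 0.32, far from proportional.

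The contradiction stands, and so does the advice not to repeat the 200 µg match in a report without checking it. What does not follow is a change to the plan. The harm is a possible sentence in a later document; no planned output makes the claim.

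The table check is also weaker than it looks. It extrapolates six-fold from the one inhaled dose shown, uses four intravenous subjects with preliminary values, and meets inhaled gCVs above 70%. On Cmax, a slope near 0.7 would bring the equivalent close to 200 µg. The fuller inhaled and intravenous results that Section 1.3 cites (Tables 1.2.4: 1 and 1.2.4: 2) are not in the public text, so the source of the 200 µg figure cannot be traced.

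One might add that 200 µg inhaled exceeds the 150 µg/day given as the highest multiple dose. That holds only if the sentence is read in inhaled equivalents. The next paragraph of Section 4.1.2 uses the same opening words for the nominal intravenous dose, and 50 µg is below 75, 150 and 1200 µg.

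**Conclusion.** This is a clerical inconsistency between two background sections, and no change to the plan follows. That Sections 1.3 and 4.1.2 disagree is certain from the text: by a factor of 1.5 to 3 on Cmax and 3 to 6 on AUC. That the table sides with Section 1.3 (347 and 673 µg) is conditional on near-proportional inhaled exposure, and is firmer on AUC than on Cmax.

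The effect on results is nil. The endpoints are recoveries relative to the dose given and exposures as measured, all summarised descriptively. The ordering against 1200 µg inhaled is unchanged at 0.29 and 0.56, and support for tolerability comes from direct use of 50 µg intravenously in 1399-0014, not from the inhaled match. By the date of the SAP (18 March 2021), all Part 1 subjects had been dosed and discharged, Part 2 had been cancelled and development had ended, so no conduct remained to alter.

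The two passages must be reconciled before either is cited as the exposure equivalence. That is a matter for whoever writes the report. No view is taken here on any dose.
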